7.1.3 ECG

Triplicate ECG recordings are required within 7 days prior to starting study treatment (i.e., during screening), as well as at the times as shown in the study plan.

Triplicate ECG recordings should be taken within an approximate 5-minute period. Additional ECGs may be taken at any other time the Investigator deems necessary for safety during the administration period. The patients will rest for at least 10 minutes before the start of each recording and they must be in the same supine body position (maximum 30 degrees flexion in the hip and feet not in contact with the footboard) at the recording time point. The Investigator or designated physician will review the paper copies of each of the timed 12-lead ECGs on each of the study days when they are collected and assess whether they are clinically significantly abnormal/ not clinically significantly abnormal. If there is a clinically significant abnormal finding, the Investigator will record it as an AE on the eCRF. For information on recording of AEs see Section 7.3. The original ECG traces must be stored in the patient medical record as source data.

A standardised ECG machine should be used and the patient should be examined using the same machine throughout the study, where feasible. ECGs will be recorded at 25 mm/sec. Attention should be paid to any detected increases in QTc interval. Patients who develop a single resting value of QTc interval of >450 msec/male and >470 msec/female or a shift from baseline of 60ms should stop taking the study treatment. Dosing can be resumed at a reduced dose after return of the resting QTc interval to pre-treatment status has been confirmed and correction of possible electrolyte imbalance has been made. Monitoring of QTc, checking and correction of abnormal electrolyte levels and renal function are advised, especially in case of severe/prolonged diarrhoea. If QTc increases markedly from baseline, but stays below the above limits, a cardiologist's advice should be sought and Sponsor should be contacted for advice and notification. The concomitant use of ondansetron (known to prolong the QTc interval in rare cases, per labelling) should be taken into account when interpreting QTc changes.

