8.4.2.4 Management of non-haematological toxicity for ceralasertib and olaparib

Acute toxicities in the all treatment arms should be managed as medically indicated, with temporary suspension of IP and initiation of supportive care as clinically indicated by the treating physician. Treatment must be interrupted if any NCI-CTCAE Grade 3 or 4 non hematologic AE occurs which the Investigator considers to be related to the administration of the study treatment(s). Treatment should not be restarted until the toxicity has resolved to Grade \leq 1.

Repeat dose interruptions are permitted, for a maximum of 28 days. Any patient who develops a Grade 3 or 4 non-haematologic toxicity that does not resolve to \leq Grade 1 within this period, should be removed from the study treatment. Once a dose is reduced, re escalation is not permitted.

A summary of the dose reduction guidance for ceralasertib and olaparib is presented earlier.

At the first occurrence of CTCAE grade 3 and 4 non-haematological toxicity, ceralasertib and olaparib should be held until resolution of toxicity. At the resolution of the first occurrence of any of these toxicities, no change must be made to dose. At the second occurrence, upon resolution of toxicity, ceralasertib and/or olaparib should be reduced by the 1st dose reduction for non-haematological toxicity to 120 mg qd for 7 days and/or olaparib 250 mg BID q 12 hours daily ([Appendix C Table 5](#) and [Appendix C Table 9](#)) Despite this change, at the third occurrence, upon resolution of toxicity, ceralasertib and/or olaparib should be reduced by the 2nd dose reduction to 120 mg qd for 4 days and 200 mg bid q 12 hours daily ([Appendix C Table 5](#) and [Appendix C Table 9](#)). If despite these changes, there is a fourth occurrence of toxicity, the patient should permanently discontinue study drug. Please note that, for each dose reduction, the investigator may choose to reduce ceralasertib or olaparib or both drugs. If only one drug is dose reduced, the second drug may be reduced as an additional step. Refer to [Appendix C Table 9](#) for specific dose modification guidance regarding non-haematological toxicity.

Appendix C Table 9: Summary of guidance on the management of non-haematologic toxicity for ceralasertib and olaparib

Toxicity	Ceralasertib and olaparib

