Any non-haematologic toxicity (CTCAE grade ≥ 3)	
1st occurrence
 
Withhold dose and monitor at least weekly for up to 28 days until recovery to \leqCTCAE grade 1 then resume at original dose level. If a clinical CTCAE give supportive measures and rule out other causes; if a laboratory AE is not resolving within two weeks contact Sponsor for guidance
 
If symptoms do not recover to \leqCTCAE grade 1, contact Sponsor and consider discontinue ceralasertib and olaparib .

	
2nd occurrence
 
Withhold dose for up to 28 days until recovery to \leqCTCAE grade 1 then resume at 1st reduced dose level for non-haematological toxicity (see Appendix C, table 4). The investigator may choose to reduce ceralasertib or olaparib or both drugs. If only one drug is dose reduced, the second drug may be reduced as an additional step if the toxicity recurs.
 
If symptoms do not recover to \leqCTCAE grade 1, contact Sponsor and consider discontinue ceralasertib and olaparib.

	
3rd occurrence
 
Withhold dose for up to 28 days until recovery to \leqCTCAE grade 1 then resume at 2nd reduced dose level for non-haematological toxicity (see Appendix C, table 4). The investigator may choose to reduce ceralasertib or olaparib or both drugs. If only one drug is dose reduced, the second drug may be reduced as an additional step if the toxicity recurs.
 
If symptoms do not recover to \leqCTCAE grade 1, contact Sponsor and consider discontinue ceralasertib and olaparib.

Toxicity	Ceralasertib and olaparib
	4th occurrence
	Off-study drug

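### Arm C: after a first related QTc prolongation of Grade 3 or higher, Section 7.1.3 allows restart only at a reduced dose, Section 8.4.2.4 and Table 9 require an unchanged dose, and nothing says which governs

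*Protocol*

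**What the plan says.** **Section 7.1.3 (Appendix C, ECG).** Study treatment stops at a single resting QTc above 450 ms in men or 470 ms in women, or at a 60 ms shift from baseline. The restart sentence reads: "Dosing can be resumed at a reduced dose after return of the resting QTc interval to pre-treatment status has been confirmed", with any electrolyte imbalance also corrected. On recording: "If there is a clinically significant abnormal finding, the Investigator will record it as an AE on the eCRF". For that it points to Section 7.3. It does not point to any dose-modification table.

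**Section 8.4.2.4 (Appendix C).** This applies to any Grade 3 or 4 non-haematological adverse event that the investigator judges related. "Treatment should not be restarted until the toxicity has resolved to Grade" 1 or lower. Then: "At the resolution of the first occurrence of any of these toxicities, no change must be made to dose". The first reduction comes at the second occurrence. The reader is sent to Table 9 "for specific dose modification guidance regarding non-haematological toxicity".

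**Appendix C Table 9.** The row covers any non-haematological toxicity of Grade 3 or higher. At the first occurrence, treatment is withheld until Grade 1 or lower, "then resume at original dose level".

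**Section 8.4 as a whole.** The opening text says doses may be modified as that section sets out. Special rules for pulmonary symptoms (8.4.2.5) and renal impairment (8.4.2.6) sit inside it. QTc and Section 7.1.3 are not mentioned anywhere in it.

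**The concern.** A site with such a patient has two direct instructions on the restart dose, and following one breaks the other. Section 7.1.3 is about this toxicity, but it sits under study assessments. Section 8.4.2.4 is the dose-modification section. It is worded to cover any related severe event, uses mandatory language, and presents Table 9 as the specific guidance. A site that opens only the dose-modification section would restart at full dose a patient for whom the ECG section allows only a reduced one. At stake is patient safety and consistent handling across sites. The efficacy analysis is not involved.

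**Working it through.** No sample size, power or error rate is involved, and the protocol gives no figure to reproduce. The check is a comparison of the rules, followed by the size of the dose gap.

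**Step 1. Do both rules reach the same patient?** Section 7.1.3 has a clinically significant ECG abnormality recorded as an adverse event. Master protocol Section 6.2.3 counts a QTcF above 470 ms or a shift of 60 ms or more among clinically significant abnormalities. Such an event, if Grade 3 or higher and judged related, also falls under 8.4.2.4 and Table 9. Below Grade 3, only 7.1.3 applies.

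**Step 2. Set the instructions side by side.**

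| | Section 7.1.3 | Section 8.4.2.4 and Table 9, first occurrence |
|---|---|---|
| Recovery needed | QTc back to its pre-treatment level, electrolytes corrected | Grade 1 or lower |
| Restart dose | Reduced | Unchanged |

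The recovery tests are compatible: Grade 1 or lower is a minimum, 7.1.3 is stricter, and a site can wait for both. The restart doses are not compatible.

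**Step 3. Is there a precedence rule?** None is stated. Section 8.4 does not carve out QTc, and 7.1.3 does not refer to Table 5 or Table 9. Arm B is handled differently: Appendix B Section 7.3.2 makes an exception for unique toxicities, and Appendix B Table 9 has its own QTc rows. Those are different drugs, so this does not settle what Arm C should say, but it shows what Arm C lacks.

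**Step 4. Size of the gap per 28-day cycle.** Section 7.1.3 names neither drug nor level. Assume its reduced dose is the next step in Appendix C Table 5, and that the unchanged dose in Table 9 is the patient's current dose.

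- From the starting dose to the first non-haematological step. Ceralasertib: 160 × 7 = 1120 mg against 120 × 7 = 840 mg; 840/1120 = 0.75, a 25% reduction. Olaparib: 300 × 2 × 28 = 16,800 mg against 250 × 2 × 28 = 14,000 mg; 14,000/16,800 = 0.833, a 16.7% reduction.
- From the first haematological step to the second step. Ceralasertib: 160 × 4 = 640 mg against 120 × 4 = 480 mg; 480/640 = 0.75, a 25% reduction. Olaparib: 14,000 mg against 200 × 2 × 28 = 11,200 mg; 11,200/14,000 = 0.80, a 20% reduction.
- From the first non-haematological step, reached for another toxicity, to the second step (if occurrences are counted per toxicity). Ceralasertib: 480/840 = 0.571, a 42.9% reduction. Olaparib: again 20%.

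The gap may apply to one drug or both, because "If only one drug is dose reduced, the second drug may be reduced as an additional step".

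**Step 5. A trap for the repair.** Table 5 labels only one ceralasertib level as non-haematological: 120 mg on Days 1 to 7. If a correction simply called for the next lower non-haematological level, a patient at 160 mg on Days 1 to 4 (640 mg per cycle) could be moved to 840 mg. As 840/640 = 1.31, that is about 31% more drug after a QTc event. The correction has to be tied to the patient's current dose.

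**The case against.** The best defence is that the specific rule governs the general one. Section 7.1.3 is written for QTc, with its own limits, stop, recovery test and restart dose, while Table 9 is a default. That is the natural reading, and it keeps the matter small. It does not dispose of it: the text never says so, and the competing instruction is mandatory and sits where sites look for dosing rules.

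The second defence is discretion. Section 8.4 lets the investigator interrupt or reduce for any toxicity. Master protocol Section 4.9 ends dosing for events that contraindicate it. Entry criteria exclude a mean QTc above 470 ms and factors that raise QTc risk. These lower the risk, and choosing the reduced dose is the cautious course. A general permission still does not cancel a direct instruction to leave the dose alone.

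Two stronger readings are tempting and should not be adopted. A reader might infer that the recovery tests also conflict; they do not, as Step 2 shows. A reader might also infer that the plan restarts severe QTc events at full dose and milder ones reduced. That requires ignoring 7.1.3 for the severe event. Section 7.1.3 has no upper limit, so both rules apply to that event and Table 9 does not simply prevail.

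**Conclusion.** The conflict is real and is confined to the restart dose after a first, treatment-related QTc prolongation of Grade 3 or higher that crosses the 7.1.3 limits. Under the Step 4 assumptions the instructions differ by 25% to 42.9% of the per-cycle ceralasertib dose, by 16.7% to 20% for olaparib, or by both. These are step sizes in Table 5, not measures of risk.

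How many of the up to 20 Arm C patients would be affected cannot be stated. The protocol gives no frequency for such events and no millisecond cut for Grade 3. Nothing here supports an inference about ORR or its analysis. This is a limited safety-wording conflict that should be corrected because the correction is simple.

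**What to change.** Add to Appendix C Section 8.4.2.4 and to the first-occurrence row of Table 9:

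*Exception: QTc prolongation meeting the Section 7.1.3 thresholds is managed under Section 7.1.3, which takes precedence. Restart only once QTc is back to its pre-treatment level and electrolytes are corrected, with a reduction from the patient's current dose: from the initial dose, to the Table 5 first non-haematological step; from any first-step dose, to the Table 5 second step; from the second step, discontinue. The total dose per cycle must not increase.*

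The sponsor should name the drug or drugs to be reduced, and Section 7.1.3 should refer to Tables 5 and 9. The later rows of Table 9 point to Appendix C Table 4 for dose levels, but that is the laboratory table; the pointer should go to Table 5.

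The cost is a small wording amendment, with no new assessments or data. If it is classed as substantial, master protocol Section 11.5 requires ethics approval, and regulatory approval where applicable, before it takes effect. It could be carried with the next amendment, with a clarification letter to sites in the meantime, a route that master protocol Section 7.9 already foresees.

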7.1.4 Laboratory safety assessment

Blood and urine samples for safety assessments will be taken at the visits as indicated in the study plan. All laboratory assessments described will be performed at the local laboratories. Additional safety samples may be collected if clinically indicated at the discretion of the Investigator.

Laboratory tests do not need to be repeated at baseline if the baseline visit is within 3 days of the screening sample. The date, time of collection and results of each collection will be recorded in the appropriate CRF.

Laboratory values that meet the criteria for CTCAE grade 3 or have changed significantly from baseline and are considered to be of clinical concern will be repeated/confirmed within 7 days and followed up as appropriate.

The following laboratory variables will be measured:

Appendix C Table 4 Laboratory safety assessment

Clinical chemistry	Haematology
Serum (S)-Albumin	Blood (B)-Haemoglobin
	B-Leukocyte
S-ALT	B-Absolute leukocyte differential count*
S/P-AST	Neutrophils
S-Alkaline phosphatase	Lymphocytes
S-Bilirubin, total	Monocytes
S-Calcium	B-Platelet count
S-Creatinine	B-Mean Cell Volume
S-Potassium	Coagulation**
S-Sodium	B-INR
S-Urea nitrogen or Urea	APTT
S- C-reactive protein	Urinalysis
S – total protein	Urine (U)-Protein/ Albumin
Pregnancy tests	U-Glucose
	U-Blood/ Hb / Erythrocytes

* If absolute differentials not available please provide % differentials

** Coagulation tests will be performed at screening and if clinically indicate. Each coagulation result will be recorded on the eCRF. Patients taking warfarin may participate in this study. However, it is recommended that INR be monitored carefully at least once per week for the first month, then monthly if the INR is stable.

The Investigator should make an assessment of the available results with regard to clinically relevant abnormalities. The laboratory results should be retained at centre as source data for laboratory variables. For information on how AEs based on laboratory tests should be recorded and reported, see Section 7.3.7 in the master protocol.

NB. In case a subject shows an AST or ALT \geq 3xULN or total bilirubin \geq 2xULN please refer to [Appendix E](#) ‘Actions required in cases of combined increase of aminotransferase and total bilirubin – Hy’s Law’ for further instructions.

Blood volumes can be found in the Laboratory Manual.

7.1.5 Bone marrow or blood cytogenetic samples

Bone marrow or blood cytogenetic samples may be collected for patients with prolonged haematological toxicities as defined in Section [Management of prolonged haematological toxicities while on study treatment](#).

Bone marrow analysis should include an aspirate for cellular morphology, cytogenetic analysis and flow cytometry, and a core biopsy for bone marrow cellularity. If it is not possible to conduct cytogenetic analysis or flow cytometry on the bone marrow aspirate, then attempts should be made to carry out the tests on a blood sample. Full reports must be provided by the investigator for documentation on the Patient Safety database. These data are not required to be entered into eCRF.

7.2 Pharmacokinetics

7.2.1 Collection of pharmacokinetic samples

The following PK sampling will be performed on Cycle 1.

- Day 1; sampling times - 1-3 hours, 3-6 hours and 6-12 hours post-treatment
- Day 7; sampling times - pre-dose and 0.5-1 hour, 1-3 hours, 3-6 hours and 6-12 hours post-treatment.

The following PK samples will be performed on Day 1 of Cycles 2 to 6 only.

- Cycle X, Day 1: Single sample 1-6 hours post treatment

Samples will be collected, labelled, stored and shipped as detailed in the Laboratory Manual. The date and time of collection of each sample will be recorded in the medical notes and eCRF. All the post-dose samples collected within 10% of the scheduled time (e.g. \pm 6 minutes for 60 minute sample) will be considered protocol compliant.

PK samples are to be taken as blood sample (4 mL) for determination of olaparib and ceralasertib concentrations in plasma. It is essential that PK blood sampling is conducted at the planned study timepoints. Patients should be instructed to fast and hold their morning dose of ceralasertib/olaparib on any day PK sampling is scheduled so it may have timed administration in the clinic. Any residual sample remaining after PK analysis has been performed may be used for exploratory biomarker research and characterisation of metabolites, if consent for this exploratory research has been obtained.

7.2.2 Determination of drug concentration in pharmacokinetic samples

Samples for determination of drug concentration will be analysed by Third party bioanalytical laboratory on behalf of AstraZeneca. Full details of the analytical methods used will be described in a separate bioanalytical report.

Pharmacokinetic samples will be disposed of after the Bioanalytical Report finalization or six months after issuance of the draft Bioanalytical Report (whichever is earlier), unless requested for future analyses. Pharmacokinetic samples may be disposed of or destroyed and anonymised by pooling. Additional analyses may be conducted on the anonymised, pooled PK samples to further evaluate and validate the analytical method. Any results from such analyses may be reported separately from the CSR.

Incurred sample reproducibility analysis, if any, will be performed alongside the bioanalysis of the test samples. The results from the evaluation will not be reported in the CSR but separately in a Bioanalytical Report. Any residual back-up PK samples may be used for future exploratory biomarker research (in this case, residual back-up PK samples will be shipped to the AZ biobank; see details in the Laboratory Manual).

7.3 Efficacy Analysis

See Section 6.1 of the master protocol.

Efficacy in Arm C will be assessed using RECIST 1.1 criteria on images collected at baseline and then at 8 weeks, then at 12 weeks and then every 8 weeks (all \pm 1 week) for the first 72 weeks and then every 12 weeks (\pm 1 week) thereafter, relative to the first day of investigational drug administration, up to objective disease progression by RECIST 1.1. After that, patients will then be followed for survival, regardless of whether study treatment is discontinued or delayed and/or protocol violations, unless they withdraw consent.

Categorisation of objective tumour response assessment will be based on the RECIST 1.1 criteria of response: CR, PR, SD and PD. Target lesion (TL) progression will be calculated in comparison to when the tumour burden was at a minimum (ie, smallest sum of diameters previously recorded on study). In the absence of progression, tumour response (CR, PR, SD) will be calculated in comparison to the baseline tumour measurements obtained before starting treatment.

7.4 Biomarker analysis

Biological samples (eg, archival tumour samples, tissue and/or blood) will be collected as detailed in the Laboratory Manual in order to carry out retrospective biomarker analysis to assess correlations with disease activity, effects of study drug, clinical outcomes and toxicity.

7.4.1

CCI

CCI

Such analysis may include, but is not restricted to:

•

CCI

- CCI [REDACTED]
- █ [REDACTED]
- █ [REDACTED]
- █ [REDACTED]
- █ [REDACTED]
- █ [REDACTED]
- █ [REDACTED]

Details of sample processing methods can be found in the study Laboratory Manual.

Results of these other exploratory analyses will not be reported in the CSR, but may be added in an appendix to the CSR. No formal statistical analysis is planned.

7.4.2 Collection of peripheral blood for pharmacodynamic biomarker analysis

Peripheral blood samples will be collected and analyzed for downstream analysis of ATR pathway biomarkers that may include but are not limited to: CCI [REDACTED] in purified peripheral blood mononuclear cells (PBMC) samples, possibly including CCI [REDACTED]. Circulating soluble factors such as cytokines that may include but are not limited to GM-CSF, M-CSF and IFN γ may be assessed. Additional details of blood collection, shipping and storage of samples for biomarker assays can be found in the laboratory manual.

Peripheral blood samples will be collected for pharmacodynamic biomarker analysis at predose on Cycle 1 Day 1, 6 hours post dose on Cycle 1 Day 7, Cycle 1 Day 15, Day 1 of each subsequent cycle and at End of Treatment. Details for processing, handling, and shipping are provided in the Laboratory Manual.

In addition, blood samples will be collected in Streck DNA BCT tubes, and processed to isolate CCI [REDACTED]. Additional samples may also be taken to generate circulating mRNA for storage and subsequent analyses. These samples will be used to assess the expression of genes and/or the presence of mutations in key driver genes and their association with response or resistance.

The timing of the pharmacodynamic biomarker samples may be adjusted during the study, dependent on emerging data, in order to ensure appropriate characterisation of biomarkers.

7.4.3 Collection of archival tumour samples

Formalin fixed tumour tissue embedded in paraffin blocks are optional for all dosed patients. If baseline biopsy samples can also be collected, retrieval of the archival diagnostic tumour material is still highly encouraged, to provide data on how the tumour has evolved since

diagnosis. Archival samples from either primary or metastatic tumour will be accepted but tissue from the primary tumour is preferred. Tissue from the most recent biopsy would be preferred where a patient has archival tissue samples from multiple time points.

Freshly prepared unstained slides (minimum 10, preferably 20), 4 micron sections from the archival tumour block are accepted if tumour blocks cannot be submitted, however tumour tissue blocks are preferred. Blocks will be repatriated to clinical sites upon request.

Details of sample collection, processing, shipping and storage will be described in the Laboratory Manual.

